## Protection of Human Subjects

The subject population for the present application will include approximately 69 individuals diagnosed with Schizophrenia or Schizoaffective Disorder, Depressed Type (collectively referred to as "SZ" patients) (ages 18-55). These numbers represent the estimated samples that will be screened in order to yield a final sample size of 54 SZ patients who will complete Aim 1, of whom 36 will also complete Aim 2. Subjects are recruited from the San Diego community, and their ethnic/ racial characteristics are described elsewhere.

Specific inclusion and exclusion criteria are as follows:

**Inclusion criteria:** 18-55 y.o. AP-medicated (stable regimen  $\geq$  1 month; current active outpatient treatment) outpatients with a primary diagnosis of SZ or schizoaffective disorder (depressed type) for  $\geq$ 2 years, clinically stable (non-acute phase  $\geq$ 12 weeks; not hospitalized in  $\geq$ 2 months; all "no" responses on C-SSRS items 1-5 (1 month) and behaviors (3 months), never treated with TCT.

**Exclusion criteria:** premorbid IQ  $<$ 70, substance abuse (past month; positive UTox), history of stimulant dependence, pregnant or nursing (women of childbearing potential consent to double-barrier contraception), history of significant medical/ neurologic illness (e.g. cancer, diabetes, CVA, heart disease, HIV, tuberculosis), history of seizure, open head injury or closed head injury with loss of consciousness  $>$  10 min, R-hand injury), vital signs (VS): SBP $<$ 90 or  $>$ 160; DBP $<$ 45 or  $>$ 95; HR $<$ 55 or  $>$ 95, hearing deficit ( $>$ 40 dB @ 1000 Hz), corrected visual acuity  $<$  20/40^12, color blindness; inability to provide informed consent or to complete visits needed for this application; past or current treatment with TCT; current medications include psychostimulants, monoamine oxidase inhibitors, or dopamine agonists (including bromocriptine and amantadine).

Patients are typically first screened by a trained laboratory assistant, who will exclude them based on the above criteria. Importantly, all SZ participants must be taking an antipsychotic medication on an ongoing basis (including depot preparations), with a stable dose for at least 1 month prior to study participation, and must be maintained on that medication throughout the study. Dose adjustments by the treating physician will be recorded. SZ patients cannot be taking a concomitant dopamine agonist medication (e.g. amantadine or bromocriptine). For appropriate subjects, the study is described again, and subjects sign consents for participation.

This age range was selected to avoid ethical and interpretative concerns associated with drug effects on symptoms and biomarkers in children and adolescents, as well as diagnostic uncertainties in younger individuals exhibiting psychotic symptoms. There will be a roughly equal representation of males and females; sample size is based on power analyses described in this application. The difference between the size of the anticipated screened population and anticipated final sample size (n=69 vs. n=36 SZ patients) reflects predicted rates of subject screen failure and attrition.

Records and data will be rigorously protected, as described below. Historical and questionnaire data, biomarker and related measures will be obtained; urine will be obtained for toxicological analysis as part of the subject exclusion process and with each study visit to reduce risk of interactions with the study drug and of uncontrolled effects on TCT performance and outcome measures.

Subject recruitment and informed consent procedures follow the PI's established methods, approved by the UCSD Human Subjects IRB. In all cases, fully informed consent is obtained by a trained technician or the PI, and the PI will be directly available to clarify questions. Signed and witnessed consents are kept on file with other subject data. The UCSD IRB has authorized no waivers or modifications of normal procedures.

Study governance follows our successful model: the PI provides study oversight, runs weekly diagnostic consensus / clinical monitoring meetings, oversees IRB and DSMB interactions, insures recruitment / testing milestones, among other roles; Co-I's oversee all biomarker testing, data fidelity and analyses (GL, MT), participate in clinical consensus meetings (GL). Our DSMB, through the UCSD CTRI, ensures patient safety and data validity and integrity (see Letter).

Potential risks are minimal. The rating scales and questionnaires are innocuous. ERP testing exposes subjects to the application of scalp electrodes and to brief sounds, which in  $>$ 25 years of testing have caused no side-effects. Alternative measures have been considered; the selection of these specific ERP measures reflects the significant advantages of applying towards these studies the substantial body of information generated by  $>$  25 years of systematic studies of ERPs in healthy and clinical populations. All other measures require only computer keyboard or paper-pencil use and involve no risk.

The AMPH dose (5 mg po) is low in terms of clinical use ("starting dose for a 6 year-old with ADHD"), and based on our substantial experience with higher doses in healthy (20 mg) and SZ populations (10 mg) (see citations in "Research Strategy"), including studies with multiple doses administered over 4 weeks, adverse reactions are not likely (never seen in our experience with over 120 HS given 20 mg p.o., or in  $>$  70 SZ patients tested thus far with 10 mg AMPH). Furthermore, higher daily doses of AMPH in SZ patients

administered over a 10-week clinical trial followed by rapid discontinuation yielded adverse event rates comparable to those of placebo. No consistent subjective effects have been associated with the 5 mg dose of AMPH in our studies, nor has 5 mg produced any statistically significant autonomic changes. Alternative drugs have been considered, and the proposed drug was selected, based on a rationale clearly described in "Research Strategy".

The use of AMPH as a daily augmentation medication for SZ patients has been reviewed in systematic meta-analyses, revealing no adverse effects (but some benefits) with AMPH; by contrast, methylphenidate was associated with adverse effects. The use of AMPH to study neurocognition and brain imaging in antipsychotic-medicated and unmedicated SZ patients has been described in numerous published reports, cited in this application. A 1982 review of the use of high doses of AMPH in about **300 unmedicated SZ patients** – mostly via an i.v. route – produced mixed changes, with most patients having no symptomatic changes, and with more patients showing improvement than worsening of symptoms. More recent case seriese.g. 21 identify predominant symptomatic improvement in AP-medicated SZ patients prescribed high daily doses of AMPH (40-80 mg po) for periods of years. In controlled trials, adverse effects after an oral dose of 10 mg AMPH, or even with 10 weeks of higher daily doses in antipsychotic-medicated SZ patients are extremely rare. Our recent review of our laboratory's experience supports the safety of AMPH in the same population to be recruited for the present application. For perspective, the present study proposes to use 5 mg AMPH, about 3 times per week, for about 10 weeks. Nonetheless, clinical state will be carefully monitored in all test subjects via symptom ratings scales described in the application. All testing will be monitored by a licensed physician, who will remain on site for the entire test day, until subject discharge; R33 patients will be evaluated by a trained Research Associate during 3x/week visits for TCT, with a specific focus on suicidality and psychotic symptoms via both unstructured and structured clinical assessment (e.g. including use of the Columbia Suicide Severity Rating Scale (C-SSRS)). Any increase in symptoms is reviewed immediately with a study Psychiatrist, who will make appropriate clinical interventions, potentially including an Emergency Room evaluation for hospitalization. Electrocardiograms will be administered at the onset, mid-point and end of the study. Follow-up contact will be attempted with all patients who miss scheduled visits. These are standard practices in the PI's laboratory, where studies of acute drug effects (e.g. memantine, AMPH) on the proposed measures in SZ patients are commonly conducted.

The overall risks of this proposal are small. AMPH will not be administered to subjects in whom it is medically contraindicated, such as subjects with known cardiovascular or neurologic disorders or diagnoses of stimulant dependence (although it is notable that oral AMPH, at doses up to 60 mg, has been investigated as a treatment for cocaine dependence). The dose selected for use in these studies is in the low- or below-therapeutic range for AMPH. Studies will be conducted under the direct supervision of a licensed physician. To address the potential for AMPH to produce changes in blood pressure, all subjects' vital signs will be carefully monitored, and subjects will not be released from the laboratory until their vital signs are within normal limits; it is notable that the dose of AMPH in this application has been tested in SZ patients in the PI's laboratory and produced minimal autonomic activation. Drugs will be dispensed by a licensed physician or pharmacist, and a licensed physician or nurse will be present on the premises at all times during testing to assess and address potential adverse drug effects, and if needed, to administer medical assistance to the test subject. Protection of subject confidentiality and privacy will be rigorously guarded by the assignment of coded numbers to each file in the computer analysis and database.

Risk/benefit ratio: Both study arms include an active intervention with documented efficacy in reducing symptoms and improving neurocognition in SZ patients. Thus, it is a reasonable likelihood that many study participants will benefit clinically from completing this study, regardless of their arm assignment. The hypothesis being tested is that these benefits will be augmented by AMPH. It is anticipated that the proposed study will yield important, new information about a new therapeutic approach in SZ patients, as well as systems-level neural information of direct relevance to several neuropsychiatric disorders. Thus, this study has a significant potential for providing major gains in our treatment and understanding of the brain basis for disorders that are severe and common. It is possible that the information obtained, and the treatment administered, in this R33 with individual subjects will be of direct benefit to them. In addition, subjects will benefit indirectly - through a cascade of familial and societal benefits - from the information generated by these studies. Furthermore, based on their awareness of the potential importance of this work to their community, subjects will benefit in areas of self-esteem and self-understanding. Information from physical examinations, and screening measures, may also be of direct benefit to test subjects. The overall risks of the proposed studies are low, as described above. Thus, on balance, the risk/benefit ratio of the proposed studies is very low.

## **Data and Safety Monitoring Board and Plan:**

The Data and Safety Monitoring Board (DSMB) is an independent group of three UCSD experts established through our UCSD CTRI, based on a Data and Safety Monitoring Plan (DSMP) specific to this R33 application. Our UCSD CTRI is partially funded by a Clinical and Translational Science Award (CTSA) from the National Institutes of Health. The DSMB comes at no cost to this application.

The DSMB consists of 3 CTRI multidisciplinary leaders, free from any conflicts of interest or direct involvement with the academic or other credit resulting from this study, who advise both the PI and the NIMH, based on their expertise. The primary responsibilities of the DSMB are enumerated below; they include to periodically review and evaluate the accumulated study data for participant safety, study conduct and progress, and efficacy, and to make recommendations to the NIMH concerning the continuation, modification, or termination of the R33 trial. The DSMB considers study-specific data as well as relevant background knowledge about the treatments (TCT and AMPH) and patient population under study (chronic psychotic disorder).

The DSMB is also responsible for maintaining the confidentiality of its internal discussions and activities as well as the contents of reports provided to it. The DSMB will review cumulative study data to evaluate safety, study conduct, and scientific validity and integrity of the trial. The CTRI has specific guidelines that ensure a comprehensive study protocol for timely DSMB notification by the PI related to any adverse events (AEs), serious adverse events (SAEs) or unanticipated problems (UPs). As part of this responsibility, DSMB members must be satisfied that the timeliness, completeness, and accuracy of the data submitted to them for review are sufficient for evaluation of the nature of the event and the safety and welfare of the study participants. The DSMB will also assess the performance of overall study operations and any other relevant issues, as necessary. **A letter of support from [name], DSMB Chair, is attached.** The “primary responsibilities” of this DSMB include:

1. Conducting an initial review of the proposed research to assure quality study conduct;
2. Reviewing study procedures to assure quality of study conduct, including SOPs for data management and quality control procedures;
3. Evaluating the quality of the ongoing study conduct by performing quarterly evaluations of the study accrual, compliance with eligibility, participant adherence to study requirements, and accuracy and completeness of data;
4. Considering factors external to the study when relevant information becomes available, such as scientific or therapeutic developments that may have an impact on the safety of the participants or the ethics of the study;
5. Recommending appropriate study review or temporary halting for any SAE, and termination due to the occurrence of 3 SAEs (symptom exacerbation or suicidality associated specifically with active treatment vs. PBO), or inability of PI to provide necessary assessment information or to answer study questions;
6. Recommending continuation of ongoing studies at quarterly reviews;
7. Considering the overall picture, including need to pursue both primary and appropriate secondary analysis, and making these recommendations during the final months of PY3 (see “Timeline”);
8. Consider modifying sample sizes based on unexpectedly robust therapeutic benefits; and
9. Reviewing final results, via DSMB report by PI within 90 days of completion of final R33 subject.

**The DSMP** proposes both the “process” and “content” of the DSMB, including its deliberative processes, event triggers that would call for an unscheduled review, stopping guidelines, unmasking (unblinding) and voting procedures prior to initiating any data review. Elements of the DSMP include:

1. How risks are minimized (e.g. see “Protection of Human Subjects” section on inclusion and exclusion criteria, careful clinical monitoring including specific scales for suicidality and psychosis and specific criteria for interventions based on these scales);
2. How risks are reasonable in relation to anticipated benefits (see “Protection of Human Subjects” re: risk/benefit ratio);
3. Plan to monitor progress and safety (see below for description of adverse events and related protocol);
4. Assessments of data quality, timeliness, participant recruitment, accrual and retention;
5. Plan to assure compliance with reporting of adverse events and/or unanticipated problems involving risk to participants or others (see below for details):

- a. Process for detecting and reporting serious and unexpected adverse events and/or unanticipated problems involving risk to participants or others;
- b. Who will be monitoring and collecting the adverse events;
- c. Who will be notified of an adverse event;
- d. The timing of reports;
- e. Annual reporting of adverse events.

This DSMP will be approved by our UCSD IRB and CTRI DSMB in advance of enrolling any R33 study subjects.

## **Adverse Events**

**Definition of Adverse Events (AEs):** An AE is defined as any untoward medical occurrence in a patient or clinical investigation subject administered a pharmaceutical product and which does not necessarily have to have a causal relationship with this treatment. An AE can therefore be any unfavorable and unintended sign (including an abnormal laboratory finding), symptom, or disease temporally associated with the use of a medicinal product, whether or not considered related to the medicinal product.

**Causal relationship of AEs:** Medical judgment will be used to determine the relationship, considering all relevant factors, including pattern of reaction, temporal relationship, confounding factors such as concomitant medication, concomitant diseases and relevant history, and reported as such to the DSMB.

**Vital signs** (measurements of systolic/diastolic blood pressure and pulse rate as outlined below) will be recorded at each study visit and at specific time points after AMPH/PBO ingestion. BP is measured using a brachial cuff on the non-dominant arm; pulse is measured manually for 30 seconds and multiplied by 2.

**Assessment of suicidality:** Suicidality will be monitored closely during the study period. Suicidal thoughts and behavior will be assessed by Columbia-Suicide Severity Rating Scale (C-SSRS). The C-SSRS is a questionnaire assessing both suicidal behavior and suicidal ideation. It consists of five questions related to suicidal behavior and five questions related to suicidal ideation, evaluated as either present or not. The C-SSRS will be administered by qualified clinicians and will be assessed at the screening visit with the aim to exclude patients with active moderate or severe symptomatology prior to the Screen Visit, or recent (or current) suicidal or suicide attempt according to the C-SSRS (baseline/screening version). Subsequently, the C-SSRS "since last visit" assessment will be performed at each visit as shown in the study Schematic. If there is a positive response of suicide attempt or suicidal ideation by the patient during the administration of the C-SSRS during the treatment period, a study MD will immediately interview the patient during the visit and determine if the patient will be discontinued from the trial and appropriate actions for the patient's safety have to be initiated. For assessment of the C-SSRS paper forms will be used and results will be transcribed into the DSMB report.

**Definition of a Serious Adverse Event (SAE):** A serious adverse event is defined as any AE which results in death, is life-threatening, requires inpatient hospitalization, results in persistent or significant disability or incapacity or is to be deemed serious for any other reason if it is an important medical or psychiatric event when based upon appropriate medical judgment which may jeopardize the patient and may require medical, psychiatric or surgical intervention.

For AEs not included in the protocol-defined grading system, the following guidelines will be used to describe severity:

- **Mild** – Events require minimal or no treatment and do not interfere with the participant's daily activities.
- **Moderate** – Events result in a low level of inconvenience or concern with the therapeutic measures. Moderate events may cause some interference with functioning.
- **Severe** – Events interrupt a participant's usual daily activity and may require systemic drug therapy or other treatment. Severe events are usually potentially life-threatening or incapacitating.

The PI's assessment of an AE's relationship to the study interventions - TCT and AMPH - is part of the documentation process, but it is not a factor in determining what is or is not reported in the study. If there is any doubt as to whether a clinical observation is an AE, the event will be reported. All AEs will have their relationship to TCT and AMPH assessed. To help this assessment, the following guidelines are used:

- Related – The AE is known to occur with TCT or AMPH, there is a reasonable possibility that TCT or AMPH caused the AE, or there is a temporal relationship between the use of TCT or AMPH and the event. Reasonable possibility means that there is evidence to suggest a causal relationship between the TCT or AMPH and the AE.
- Not Related – There is not a reasonable possibility that the administration of TCT or AMPH caused the event, there is no temporal relationship between the use of TCT or AMPH and the event onset, or an alternate etiology has been established.

The PI will be responsible for determining whether an AE is expected or unexpected. An AE will be considered unexpected if the nature, severity, or frequency of the event is not consistent with the known risks of TCT or AMPH.

AE's will be identified either 1) if alerted by study subject, their representative (relative, physician) between study visits, or 2) by careful clinical assessment at a study visit or follow-up visit. All subjects are evaluated clinically at every visit (approx. 3 times per week), and any deviation from their expected baseline clinical state will warrant a more detailed clinical assessment, documentation and intervention as necessary.

Any medical or psychiatric condition or symptom that is present at the time that the participant is screened will be considered as baseline and not reported as an AE. However, if the study participant's condition deteriorates at any time during the study, it will be recorded as an AE.

Changes in the severity of an AE will be documented to allow an assessment of the duration of the event at each level of severity to be performed. AEs characterized as intermittent require documentation of onset and duration of each episode.

The PI will record all reportable events with start dates occurring any time after informed consent is obtained until 7 (for non-serious AEs) or 30 days (for SAEs) after the last day of study participation (12 weeks post-TCT). At each study visit, the investigators will inquire about the occurrence of AE/SAEs since the last visit. Events will be followed for outcome information until resolution or stabilization.

AE's suspected by study staff are immediately reported to a study MD. A study MD (typically the PI, but other licensed MD's are also listed on this PI's IRB protocols and can provide back-up coverage) is on the premises at all times that experiments and TCT training are in progress, and study staff have cell phone access to study clinicians at all times, including weekends and holidays. If an AE is confirmed, the PI is notified immediately; study staff and clinicians have cell phone access to the PI at all times, including weekends and holidays.

The PI will convene a phone- or face-to-face meeting of all study clinicians 24 hours to discuss the implications of the AE and all necessary follow-up and interventions. A full report to the DSMB and IRB will be made within 7 days of the AE. The PI is responsible for signing off on all AE reports. Reporting lines are as follows:

Reporting Source → Research Staff → Study MD (PI) → DSMB, IRB

Reporting lines will be as above, for AEs. However, the PI will notify the DSMB and IRB in real-time in the event of any SAE; in addition, the PI will complete an SAE Form within the following timelines:

All deaths and immediately life-threatening events, whether related or unrelated, will be recorded on the SAE Form and submitted to the NIMH within 24 hours of site awareness. Other SAEs regardless of relationship, will be submitted to the NIMH within 72 hours of site awareness.

All SAEs will be followed until satisfactory resolution or until the PI deems the event to be chronic or the adherence to be stable. Other supporting documentation of the event may be requested by the NIMH as soon as possible.

Incidents or events that meet the OHRP criteria for unanticipated problems (UPs) require the creation and completion of an UP report form. It is the PI's responsibility to report UPs to the UCSD IRB and to the NIMH. The UP report will include the following information:

- Protocol identifying information: protocol title and number, PI's name, and the IRB project number;
- A detailed description of the event, incident, experience, or outcome;
- An explanation of the basis for determining that the event, incident, experience, or outcome represents an UP;
- A description of any changes to the protocol or other corrective actions that have been taken or are proposed in response to the UP.
- UPs that are SAEs will be reported to the UCSD IRB and to the NIMH within 24 hours of the investigator becoming aware of the event.
- Any other UP will be reported to the UCSD IRB and to the NIMH within 72 hours of the investigator becoming aware of the problem.
- All UPs will be reported in real time to the DSMB

Pregnancy: As described in "Protection of Human Subjects", women of childbearing years participate in the present study only under specific conditions designed to minimize the possibility of pregnancy, and with weekly or more often monitoring of urine pregnancy tests. Any patients testing positive in this surveillance will receive further study drug. The study blind will be broken; if the subject was receiving active drug, they will be referred for appropriate pregnancy-related care and follow-up will be maintained with the subject through to completion of pregnancy.

Amphetamine carries a teratogenic risk classified as Pregnancy Category C. However, the level of exposure in the present study is very low and likely to be greatly exceeded by the teratogenic risk of other medications being taken by schizophrenia patients. TCT has no known teratogenic risk.

Study Halting: Administration of study agent will be halted if three grade 3 AEs determined to be "probably related" are reported to the DSMB. The DSMB will notify the NIMH immediately when the third grade-3 event is reported and enrollment screens will stop accepting new study participants. The DSMB will convene an ad hoc meeting by teleconference or in writing as soon as possible. The DSMB will provide recommendations for proceeding with the study to the NIMH. The NIMH will inform the FDA of the temporary halt and the disposition of the study.

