**Fig. 3. Preliminary studies:** AMPH dose-effects. A. Maximal APS learning with 5 mg AMPH ( $d=0.85$ ); hatched bar shows 10 mg data from Fig. 2D. Similar effects of 5 mg were detected 60 and 210 min post-pill. B. AMPH gains in APS learning in patients with impaired-range A/V scores. C. QuickSIN detected deficits at 5 dB in low-attention patients (\*) corrected by 5 mg AMPH (!). D. Similar inverted-U AMPH effects on prepulse inhibition (PPI) in low-attention patients.

**Safety of AMPH in AP-medicated SZ patients:** Over the course of studies in Figs. 2-3, we accumulated enough experience to publish findings on the safety of AMPH in antipsychotic-medicated SZ patients. We assessed autonomic, subjective and clinical measures after acute (same day) and subacute exposure (across 4 weeks of repeated within-subject dosing), and were able to recontact and clinically assess 19 subjects with an average post-AMPH interval of 17 months. AMPH was associated with no detrimental subjective, autonomic or clinical changes. Symptoms assessed acutely, sub-utely or long-term were either unchanged or reduced. Reductions in BPRS psychosis scores were noted across each test day; long-term, psychosis symptoms declined (SAPS:  $p<0.009$ ) and function increased (Scale of Function:  $p<0.015$ ). Anecdotally, 4 subjects participated in both single and multi-dose studies, resulting in a cumulative AMPH dose of 27.5 mg; in these subjects, long-term reductions in SANS and SAPS were  $d=1.11$  and 0.93, respectively. Among the 19 recontacted subjects, antipsychotic dose (chlorpromazine equivalents) declined for 6 subjects by an average of 411 mg/d, increased in 2 subjects by an average of 146 mg/d, and was unchanged in 11 subjects. **No subjects experienced any adverse effects of AMPH after 1 dose, 3 weekly doses over 4 weeks, or both, assessed daily, weekly or 17 months later.**

For perspective, the 5 mg dose proposed in this application is a conservative starting dose for **children**, ages 6 and older, for the treatment of ADHD, who then titrate to substantially higher doses taken daily for years; this application proposes this 5 mg dose for **adults** who are taking medications (antipsychotics) known to block many adverse effects of amphetamine, and these patients will have a total exposure of 30 pills over 10 weeks.

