## Inclusion of Women, Minorities and Children

**Inclusion of women:** Women will be included in this study. There are sex differences in the DA-releasing effects of AMPH, that might impact the effects of AMPH on a number of behavioral measures that are relevant to this application. Thus, while no sexual dimorphism has been reported in the therapeutic effects of TCT, and none were noted in our study of AMPH effects on APS learning, we will strive to include enough men and women in the study to conduct meaningful analyses of sex effects on both AMPH sensitivity and biomarker predictors of AMPH effects on APS learning. To control for potential effects of menstrual cyclicity on biomarkers or drug sensitivity, Aim 1 drug testing will begin within days 1 - 7 of menses onset (our standard protocol for over a decade e.g. 106). There is a strong rationale for assessing the predicted drug effects in both men and women, because these findings will have implications in terms of the potential clinical applications of this PACT design.

[figure not shown]
Several steps will be taken to avoid exposure of any fetus to amphetamine. First, females who are pregnant, nursing, imminently planning pregnancy or have a positive urine pregnancy test on screen day or any test day will be excluded from this study. Second, female subjects of childbearing potential (defined here as any female who has not had a total hysterectomy and/or bilateral oophorectomy, or who has had a menstrual cycle within the past year) will have urine pregnancy tests weekly through the 10th week of TCT ("Surecheck Early Pregnancy Test"). Second, in all subjects of childbearing potential, Aim 1 testing will begin within days 1 - 7 of menses onset. Third, to participate in this study, females of childbearing potential must agree to use a double-barrier method of contraception when participating in sexual intercourse (regardless of other methods of contraception). If a female of childbearing potential becomes pregnant during the study, the subject will be exited from the study. The investigator will determine whether the subject was exposed to active study drug or placebo, and notify the subject of this information.

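### The pregnancy paragraph tells staff to keep giving study drug after a positive test, contradicting the rule that a pregnant subject leaves the study; a "no" has almost certainly been dropped.

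*Protocol*

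**What the plan says.** The Protocol deals with pregnancy during the trial in several places.

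- **Adverse Events, Pregnancy paragraph.** After describing urine testing weekly or more often, it gives the action on a positive result: "Any patients testing positive in this surveillance will receive further study drug". It continues: "The study blind will be broken; if the subject was receiving active drug, they will be referred for appropriate pregnancy-related care", with follow-up to the end of the pregnancy.
- **Adverse Events, the text that follows.** "Amphetamine carries a teratogenic risk classified as Pregnancy Category C". The protocol adds that exposure in this study is very low and probably outweighed by the risk from patients' other medications.
- **Inclusion of Women, Minorities and Children.** The purpose is stated first: "Several steps will be taken to avoid exposure of any fetus to amphetamine". Women who "have a positive urine pregnancy test on screen day or any test day will be excluded from this study". For a pregnancy arising later: "If a female of childbearing potential becomes pregnant during the study, the subject will be exited from the study". Then: "The investigator will determine whether the subject was exposed to active study drug or placebo, and notify the subject of this information".
- **Protection of Human Subjects.** Pregnancy is an exclusion criterion, with consent to double-barrier contraception. No rule is given for a pregnancy that arises after entry.
- **General Clinical Monitoring (Research Strategy).** A positive pregnancy test goes promptly to the on-site psychiatrist. Whether drug stops or continues is not stated.

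The SAP does not mention pregnancy.

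**The concern.** The sentence in the Adverse Events section is the operative instruction for what happens to dosing after a positive test. Read as it stands, dosing goes on. The inclusion section removes the subject from the study, which ends dosing.

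If the Adverse Events sentence were followed literally for a woman in the amphetamine arm, it would produce the fetal exposure that the inclusion section sets out to prevent. The Data and Safety Monitoring Plan refers to the adverse-event text, and that plan is to be approved by the IRB and the DSMB before enrolment. The wrong instruction therefore sits in safety text on which oversight bodies rely.

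The point concerns participant safety and consistency of the documents. It does not touch the trial's inference.

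**Working it through.** The plan gives no figure on this point, so there is none to reproduce. The check is a comparison of wording, followed by a simple count of what the wording would mean in doses.

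**1. Is the sentence current, complete text?** It is grammatical, carries no redaction mark or visible gap, and is not part of an amendment log. A word lost when the PDF was read cannot be ruled out from the text alone, but nothing at that point suggests it.

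**2. The instructions side by side**

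| Place in Protocol | Action on pregnancy or a positive test | Drug afterwards |
|---|---|---|
| Adverse Events, Pregnancy, action sentence | Further study drug given | Continues |
| Adverse Events, Pregnancy, next sentence | Blind broken; care arranged if on active drug | Implies it has stopped (past tense) |
| Inclusion of Women, positive test on screen or test day | Excluded | None |
| Inclusion of Women, pregnancy during the study | Exited, told which treatment she had | None |
| Protection of Human Subjects | Bar at entry only | Not addressed |
| General Clinical Monitoring | Psychiatrist reviews | Not addressed |

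Only the first row has dosing continue.

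**3. Does one missing word explain it?** Inserting *no* before *further* brings the first row into line with every other row. The word *further*, the past tense of the next sentence, the unblinding and the referral all fit stopping the drug. No part of the protocol gives a reason to continue dosing a pregnant subject. The dropped negation is an inference, but a strong one.

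**4. Would staff be led to the right rule?** Not directly. The Pregnancy paragraph refers readers to Protection of Human Subjects, which has the entry criterion but no exit rule. The exit rule is in the inclusion section.

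**5. What literal compliance would mean.** Inputs: 5 mg per dose, three times a week for about 10 weeks (Research Strategy, Approach), and "these patients will have a total exposure of 30 pills over 10 weeks" (Preliminary Studies, safety of amphetamine). Assumptions: exactly three sessions a week, the weekly test read after that week's sessions, and the patient continuing to session 30.

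Planned training-phase exposure: 30 × 5 mg = 150 mg.

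Doses remaining after a positive test at week *k*: 30 − 3*k*.

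| Positive test after week | Doses remaining | Amphetamine | Under the exit rule |
|---|---|---|---|
| 1 | 30 − 3 = 27 | 27 × 5 = 135 mg | 0 |
| 5 | 30 − 15 = 15 | 15 × 5 = 75 mg | 0 |
| 9 | 30 − 27 = 3 | 3 × 5 = 15 mg | 0 |

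Patients on placebo would have no amphetamine exposure either way. The documents give no pregnancy rate, so these are amounts per affected patient and not expected totals.

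**The case against.** The strongest reply is that this is a drafting slip that corrects itself. The right rule stands elsewhere in the same protocol. The next sentence makes sense only if dosing has stopped. A psychiatrist reviews every positive test, and pregnancy is an exclusion criterion. For harm to follow, staff would have to break the blind, confirm active drug, refer the patient for pregnancy care, disregard the exit rule and then hand her another pill. The dose counts describe a scenario nobody intends, and testing may be more frequent than weekly. The protocol also plays down the risk at this exposure. The missing word may be an artefact of PDF reading. The SAP's project modification is written largely in the past tense, so a correction may come late.

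Much of this is fair. The intent is recoverable, competent staff would very probably stop the drug, and the dose counts only illustrate. The possible PDF artefact is why the source should be checked first.

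The contradiction remains, however. The psychiatrist review does not say what to do about drug, the exclusion criterion operates at entry, and the paragraph's own cross-reference does not reach the exit rule. The remark that exposure is very low could even be misread as tolerating continued dosing. A stopping instruction should not depend on the reader noticing that it must mean its opposite. If dosing has ended, the record still needs correcting.

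**Conclusion.** The concern holds. The action sentence in the Pregnancy paragraph states the reverse of the exit rule in the inclusion section and of what its own next sentence implies. It should be corrected because it governs dosing after a positive pregnancy test.

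The size per affected amphetamine-arm patient runs from 135 mg (after week 1) to 15 mg (after week 9) of avoidable exposure if the sentence is obeyed literally, under the scheduling assumptions above. The number of patients affected cannot be estimated and may well be zero.

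The conclusion that the words conflict is firm on the text supplied. That a *no* was dropped is inferred from context. Whether it is missing from the sponsor's own file depends on checking that file.

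**What to change.** Check the sentence in the source document. If the negation is missing there, amend it to state that any patient who tests positive receives no further study drug and is exited from the study. Keep the existing wording on unblinding, referral and follow-up. If dosing has already finished, correct the record and have the sponsor confirm that no positive test was followed by further study drug.

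The cost is a one-sentence wording correction. Design, sample size and analysis do not change.
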